#### **5.4.10.2. Clinical Laboratory Parameters**

The following laboratory analyses will be performed at the Study Site/Clinic laboratories and recorded on the eCRF:

- Serology: HCVAb, HBsAg, HBcAb, HBsAb and HIV tests (SCV 1 only)
- Urine Drug Screen: Alcohol, amphetamines, cocaine, or phencyclidine (SCV1 only)
- Screening for tuberculosis (QuantiFERON test) at SCV1 only (optional)
- Screening for pregnancy (urine  $\beta$ -HCG) at SCV1 only.

The Study Site/Clinic laboratories will also perform Hematology, Clinical Chemistry and Urinalysis tests to support clinical management and decision-making, but these tests will not be recorded on the eCRF and will not be analyzed as part of this SAP.

The following tests will be performed by the central lab in peripheral blood samples:

- CRP
- Lipid panel (total cholesterol, LDL-cholesterol, HDL-cholesterol, triglycerides)
- Anti-rilonacept (anti-KPL-914) antibody
- KPL-914 drug levels
- Biomarkers

CRP testing will be performed for the purposes of efficacy analyses described in the Section 5.4.9.1 above.

Analysis of anti-rilonacept antibodies is described in the section 5.4.10.3 below.

Laboratory evaluation results for lipid panel, as well as changes from baseline will be summarized descriptively by visit. Only subjects with both non-missing baseline and time point values will be summarized at each time point.

Lipid panel results will be summarized both in the conventional units (mg/dL) and SI units (mmol/L).

Shifts among normal, low and high results (as determined by laboratory normal ranges) from baseline to last available post-baseline assessment in the Treatment Period and in the Extension Period will be summarized.

All individual subject clinical laboratory evaluation results that are captured in the study database will be presented in listings subject and visit.

Results of serology tests, drug screen, anti-rilonacept antibodies, tuberculosis screening, pregnancy test will be listed.

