#### **5.4.10.5. Electrocardiogram (ECG)**

Twelve-lead ECGs will be performed at screening (SCV1 and SCV2), at Study Site/Clinic visits during the Treatment Period (Interval Evaluation Visit [if applicable] and Visit 7/End-of-Trial), at the Interval Evaluation Visit during the EP [if applicable], and at the Final Study Visit/Visit 8.

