##### **Analysis based on local read**

Frequency table for interpretation (normal, abnormal not clinically significant, and abnormal clinically significant) will be generated.

Shift table for shifts from baseline to the last post-baseline assessment in the treatment period and extension period in the overall interpretation based on local read will be created.

All ECG data will be provided as a by-subject listing.

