**Kiniksa Pharmaceuticals Corp**  
**Rilonacept**  
**Statistical Analytical Plan Final 04Jun2019 Protocol No. KPL-914-C001**

**Statistical Analysis Plan**

Trial Period →	Pre-screening Period	Run-In Period (Up to 3 days)		Treatment Period (6 weeks)								Extension Period (18 weeks)			
Visit Days/Weeks →		Day -3 to Day 0 a		Day 0 b	Week 2 c	Week 3 c	W3-W4 d	Week 4 c	Week 5 c	Week 6 ee	Week 6/ End-of-Trial c			W15-W20 t	Week 25 (Week 7 +18 weeks)
Visit Number →		SC Visit 1	SC Visit 2	Visit 1 Clinic	Visit 2 (Outpt)	Visit 3 (Outpt)	Optional Interval Evaluation Visit (Clinic)	Visit 4 (Outpt)	Visit 5 (Outpt)	Visit 6 (Outpt)	Visit 7 Clinic	Monthly Visits (Outpt)	Un-scheduled Visits (Clinic)	Optional Interval Evaluation Visit (Clinic)	Visit 8 (Final, Clinic)
Dose Number →			Dose 1	Dose 2	Dose 3	N/A	Dose 4	Dose 5	Dose 6						
Unscheduled Visitsu															
Clinical laboratory tests (incl CRP) – Central laboratory 		X	X	(X) x	X	X	X	X	X	X	X	X	X	X	X
Clinical laboratory tests (lipid panel) – Central Laboratory				X								X aa			X
Clinical laboratory tests (incl CRP) – Study Site/Clinic laboratory m	X y	X	X	(X) x			X				X		X	X	X
Biomarker testing, PK, and anti-rilonacept antibody – Central Laboratory 		X		(X)	X	X	X	X	X	X	X	X	X	X	X

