- s. Adult subjects only. Subject global assessment of overall well-being will be assessed using a validated QoL Questionnaire (see Section 8.3). The assessment will be performed on-site during clinic visits. If SCV2 occurs at a different day than Visit 1 (Day 0), the global assessment will also be performed at Visit 1, prior to Study Drug administration.
- t. Subjects may return for an optional EP Interval Evaluation Visit at the clinic between Week 15 and 20 (8 to 13 weeks after Visit 7), as determined by the Investigator.
- u. Subjects reporting worsening of pericarditis symptoms or AEs may be brought in at the discretion of the Investigator for an Unscheduled Visit at any time during the Treatment Period. Any subject who is not responding to treatment (e.g., no reduction in pericardial pain compared to baseline, no decrease in CRP levels, etc.) and who is therefore considered by the Investigator to be a “Treatment Failure” may be withdrawn from further Study Drug treatment at the discretion of the Investigator and receive rescue therapy for their pericarditis according to standard of care as per Investigator decision; these subjects will be followed for safety for the remainder of the 6-week Treatment Period.
- v. At weekly Investigator (or designee) phone calls/virtual visits during the Treatment Period, Study Drug compliance, medication diary compliance, and laboratory sample collection will be checked. The subjects will be asked using non-leading questions about any AEs occurring since the last contact (phone call/virtual visit or site visit), and NRS pain assessment will be performed. Investigator (or designee) phone calls/virtual visits will be performed monthly during the EP to perform NRS pain assessments, collect AE information, and review pericarditis/concomitant medications. If scheduled, in-person Study Site/Clinic Visits (Unscheduled Visits or Evaluation Visits) can replace the phone calls/virtual visits.
- w. During the Extension Period, Study Drug treatment is weekly by self-administration, and the study nurse visits to the home and Investigator (or designee) phone calls/virtual visits are monthly.
- x. Visit 1 will coincide with SCV2. In case Visit 1 is separated from SCV2, SCV2 clinical laboratory blood sampling and subject NRS pericardial pain rating must be repeated prior to Study Drug dosing.
- y. Per Standard of Care.

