- z. Adult subjects only. The dosing preparation and administration questionnaire must be completed in the presence of Study Staff (via virtual visit) or visiting nurse.
- aa. This lab will be drawn only during the first monthly Extension Period visit.

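### The lipid and local-read ECG shift tables use only the last post-baseline result in each period, so an earlier abnormality that is normal at the end of the period is counted as no shift

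*SAP*

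**What the plan says.** Lipids (SAP 5.4.10.2). Shifts among low, normal and high are to be tabulated "from baseline to last available post-baseline assessment in the Treatment Period and in the Extension Period will be summarized". The other lipid table is continuous: "Laboratory evaluation results for lipid panel, as well as changes from baseline will be summarized descriptively by visit". Under the same section, site haematology, chemistry and urinalysis are not analysed, so lipids are the only laboratory safety panel summarised against normal ranges.

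Lipid sampling (SAP 8.1). The row "Clinical laboratory tests (lipid panel) – Central Laboratory" is marked at Visit 1, in the monthly Extension Period column and at Visit 8. Footnote aa limits the monthly mark: "This lab will be drawn only during the first monthly Extension Period visit".

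ECG (SAP 5.4.10.5). The local-read analysis plans a "Shift table for shifts from baseline to the last post-baseline assessment in the treatment period and extension period in the overall interpretation". Besides screening, tracings are taken "at Study Site/Clinic visits during the Treatment Period (Interval Evaluation Visit [if applicable] and Visit 7/End-of-Trial", at the optional Extension Period interval visit and at Visit 8.

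No worst-value or any-time shift is planned for either. Section 5.1 keeps unscheduled results out of by-visit tables; they appear in listings.

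**The concern.** Readers use a safety shift table to see whether subjects who started normal became abnormal on study. A last-value rule answers a narrower question: where each subject stood at the end of the period. When a period holds more than one result, a later normal value replaces an earlier abnormal one, and the subject is counted as unchanged.

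For lipids this affects half of the scheduled post-baseline data: the first-month draw does not enter the categorical table for anyone who also has Visit 8. The by-visit minimum and maximum may reveal an extreme value, but not how many subjects left the normal range, nor whether they were normal at baseline.

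The SAP takes a different line for other safety data. Section 5.4.10.1 counts adverse events at highest severity. Section 5.4.10.3 presents antibody status overall as well as by visit, with titres for anyone who has at least one positive sample.

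**Working it through.** The SAP gives no figure for this point, so there is nothing to reproduce. The check counts assessments per period and then illustrates the effect.

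**Step 1. Scheduled post-baseline assessments (SAP 8.1 and 5.4.10.5)**

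| | Treatment Period | Extension Period |
|---|---|---|
| Lipids | 0 | 2 (first monthly visit, Visit 8) |
| ECG | 1 fixed (Visit 7) + 1 optional | 1 fixed (Visit 8) + 1 optional |

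With one result in a period, last and worst are the same and nothing is lost. They can differ for Extension Period lipids, and for ECG only when an optional interval or unscheduled tracing precedes Visit 7 or Visit 8. The Treatment Period lipid shift has no scheduled post-baseline result to fill it.

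**Step 2. Illustration for two lipid draws**

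Assumptions, none of them in the SAP: probability p of a high result, the same at each draw, and within-subject correlation phi between the draws. Baseline status is ignored.

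- P(both high) = p² + phi·p(1−p)
- P(ever high) = 2p − P(both high)
- Shown by the last-value table = p
- Missed share of the ever-high = 1 − p / P(ever high)

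At p = 0.20 and phi = 0.5: P(both) = 0.04 + 0.5 × 0.16 = 0.12; P(ever) = 0.40 − 0.12 = 0.28; missed share = 1 − 0.20/0.28 = 28.6%.

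| p | phi | Ever high | Shown by last value | Missed share |
|---|---|---|---|---|
| 0.20 | 0.3 | 31.2% | 20% | 35.9% |
| 0.20 | 0.5 | 28.0% | 20% | 28.6% |
| 0.20 | 0.7 | 24.8% | 20% | 19.4% |
| 0.10 | 0.3 | 16.3% | 10% | 38.7% |
| 0.30 | 0.7 | 36.3% | 30% | 17.4% |

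The last two rows are the extremes for p from 0.10 to 0.30 and phi from 0.3 to 0.7. With independent draws (phi = 0) the missed share is 1 − 1/(2 − p): 47.4% at p = 0.10 and 41.2% at p = 0.30.

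**Step 3. In subjects**

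The fraction high at the first draw and not high at the second is p(1−p)(1−phi). Over the same grid it runs from 0.10 × 0.90 × 0.3 = 0.027 to 0.30 × 0.70 × 0.7 = 0.147. If all 40 planned subjects had both draws, that is about 1 to 6 subjects. This is an upper bound, because the Extension Period is optional and offered only to responders.

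**Step 4. What a worst-value rule does when nothing changes**

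Use the same model with no drug effect, p = 0.20 and phi = 0.5. A single baseline draw is high in 20% of subjects, the last draw in 20% and the worst of two in 28%. The worst-value comparison therefore shows a net 8-point worsening from looking twice, while the last-value comparison shows none.

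**The case against.** The last-value rule is clear and reproducible, and end-of-period status is a legitimate question in a descriptive pilot of up to about 40 subjects. Much of the case against changing it stands:

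- A reader might infer that the first-month lipid results are thrown away. They are not. They enter the by-visit descriptive statistics, including minimum and maximum, and the listings. What is missing is a count by category.
- A reader might infer that the rule biases the table towards no harm. The illustration does not show that. It contains no recovery or treatment effect, so its missed share is only the difference between one look and two. Step 4 shows that worst-of-two against one baseline overstates worsening, and there is no control arm to calibrate it.
- A reader might infer that the last lipid value tends to be off drug, or lowered by treatment. The SAP supports neither. Footnote u of 8.1 says of withdrawn Treatment Failures that "these subjects will be followed for safety for the remainder of the 6-week Treatment Period", but no post-baseline lipid sample is scheduled in that period. The SAP does not describe off-drug Visit 8 lipids and does not mention lipid-lowering therapy. Footnote u could matter for a Treatment Period ECG, but not for lipids.
- Section 2.2 encourages stopping NSAIDs and colchicine within 15 days of entering the Extension Period, and corticosteroids by Week 12. The first monthly draw can fall within that weaning and Visit 8 (Week 25) after it. The draws are therefore not interchangeable, but this does not favour the worst value over the last.
- For ECG, the central read is tabulated normal/abnormal by visit, 5.4.9.4 counts ST-elevation and PR depression by visit from the local read, and there is a local-read frequency table. Such ECG changes can also reflect the pericarditis itself.

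These points limit the claim without removing it. No planned table counts how many subjects had a transient lipid abnormality, and the by-visit ECG tables omit unscheduled tracings.

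**Conclusion.** The point holds in limited form. Both shift tables show end-of-period status only. For lipids, a first-month high or low result that is normal at Visit 8 is counted as no shift, and no other table gives it by category. Under the assumed p and phi this omits 17% to 39% of subjects ever high, at most about 1 to 6 of 40. The SAP supplies neither p nor phi, and the calculation ignores baseline status, so these figures show scale only. For ECG the loss depends on an optional or unscheduled tracing preceding the fixed visit, and other by-visit tables partly cover it.

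The last-value rule is not an error and should stay. A worst-value shift beside it is a cheap improvement that uses collected data and fits how the SAP handles adverse events and antibodies. Separately, the Treatment Period lipid shift in 5.4.10.2 does not match the schedule and needs reconciling.

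**What to change.** 1. In 5.4.10.2 and the local-read part of 5.4.10.5, keep the last-value shift and add a shift from baseline to the worst post-baseline result in each period, using all available assessments including unscheduled ones. For lipids, take the highest total cholesterol, LDL-cholesterol and triglycerides and the lowest HDL-cholesterol. For ECG, rank abnormal clinically significant above abnormal not clinically significant above normal.
2. For lipids, also tabulate the shift at each scheduled draw (first monthly visit and Visit 8). This compares one draw with one draw and shows abnormalities in either direction.
3. Footnote the worst-value table: the worst of several results against a single baseline shows more apparent worsening by chance, and there is no control arm.
4. Reconcile the Treatment Period lipid shift with 8.1: remove that table, or correct the schedule if a sample is in fact taken in that period.

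The cost is a few sentences in the SAP, one more derived record per parameter and period, and some extra table columns. No new data are needed. The downside is the chance inflation, which the retained last-value shift and the footnote keep in view.

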#### **5.4.10.3. Anti-rilonacept (anti-KPL-914) antibodies**

Anti-rilonacept antibodies will be measured in blood samples collected at SCV1/Day 0, Visit 2, Visit 3, Visit 4, Visit 7, EP Month 2, and Visit 8.

Number and percentage of subjects with positive and negative anti-rilonacept antibodies will be presented overall, and by visit for subjects in each Part and for all Parts combined. For subjects with at least 1 positive sample, number and percentage of subjects with each observed titer will be presented.

In addition, a listing with anti-rilonacept antibody status (positive, negative), and antibody titer (for subjects with positive anti-rilonacept antibodies) will be provided by visit.

Additional analyses may be performed, including anti-rilonacept antibodies transience, persistence, or temporal association with efficacy or safety measures.

#### **5.4.10.4. Vital Signs**

Vital signs will be recorded at Study Site/Clinic visits in a standardized manner, i.e., after the subject has rested in the sitting position for 5 minutes.

The following measurements will be taken: oral temperature, respiratory rate, blood pressure, and pulse. Overall interpretation (normal, abnormal not clinically significant or abnormal clinically significant) will also be recorded.

Body weight and height will be determined and BMI will be calculated at SCV1 and at the final study visit.

Actual values of vital signs (including weight and BMI) and changes from baseline will be summarized using descriptive statistics by visit. Only subjects with both non-missing baseline and visit values will be summarized at each visit.

Overall interpretation will be summarized categorically by visit.

All vital signs data will be provided as a by-subject listing.

#### **5.4.10.5. Electrocardiogram (ECG)**

Twelve-lead ECGs will be performed at screening (SCV1 and SCV2), at Study Site/Clinic visits during the Treatment Period (Interval Evaluation Visit [if applicable] and Visit 7/End-of-Trial), at the Interval Evaluation Visit during the EP [if applicable], and at the Final Study Visit/Visit 8.

##### **Analysis based on central read**

Heart rate (bpm), PR Interval, RR Interval, QRS Interval, QT Interval, QTcB Interval, QTcF Interval (msec) and the overall interpretation (normal, abnormal) will be captured.

Actual values and changes from baseline for the ECG intervals and heart rate will be summarized using descriptive statistics by time point using central ECG reads.

Number and percentage of subjects with normal and abnormal overall interpretation, with further breakdown by abnormal findings (such as conduction, rhythm, ST segment and T wave findings) will be presented by visit.

##### **Analysis based on local read**

Frequency table for interpretation (normal, abnormal not clinically significant, and abnormal clinically significant) will be generated.

Shift table for shifts from baseline to the last post-baseline assessment in the treatment period and extension period in the overall interpretation based on local read will be created.

All ECG data will be provided as a by-subject listing.

#### **5.4.10.6. Physical Examination**

Physical examinations will be performed at screening (SCV1 and SCV2), at Study Site/Clinic visits during the Treatment Period (Interval Evaluation Visit [if applicable] and Visit 7/End-of-Trial), at the Interval Evaluation Visit during the EP [if applicable], and the Final Study Visit/Visit 8.

Physical examination will include assessment of the following systems: HEENT, Neck/Thyroid, Respiratory/Chest, Cardiovascular, Abdominal, Urological, Lymph Nodes, Skin, Musculoskeletal/Extremities and Neurological. Additional body systems may be evaluated at the investigator's discretion. Each body system will be characterized as Normal, Abnormal Not Clinically Significant or Abnormal Clinically Significant.

Physical examination findings will be summarized by visit. The number and percentage of subjects with normal, abnormal not clinically significant and abnormal clinically significant findings will be presented for each body system.

All physical examination data will be provided in a listing.

#### **5.4.10.7. Pain/Rescue Medication Use**

Number and percentage of subjects who used Pain/Rescue medication at least once will be presented for the Treatment Period, Extension Period and entire study broken down by the medication type as captured on the eCRF (opioid analgesics, non-opioid analgesics, acetaminophen, other). Medication used at fixed doses and as needed (PRN) will be counted in analyses.

Time to first Pain/Rescue medication will be defined as the earliest study day when a rescue medication is taken post-baseline. For subjects who never took any rescue medication post-baseline, it will be censored at the study day of study completion/discontinuation. Kaplan-Meier estimates of the median, 25% and 75% percentiles of time to first rescue medication will be provided with 95% confidence intervals using the same methods as for time for CRP normalization (see Section [5.4.9.1](#)).

All Pain/Rescue medications will be listed.

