**Extension Period (EP):** The EP is defined as the 18 weeks following the Treatment Period. Subjects who are considered to be “Treatment Responders” will be, at the discretion of the Investigator, offered participation in an optional 18-week EP, in which weekly administration of open-label KPL-914 may be continued for a total duration of 24 weeks. The weekly KPL-914 doses will be by self-administration or administered by adequately trained caregiver, and study nurse visits to the subject’s home as well as Investigator (or designee) telephone calls/virtual visits will continue on a monthly basis. During the EP, the Investigator is encouraged to wean concomitant NSAIDs, and/or colchicine, and/or corticosteroids. It is encouraged that NSAIDs and colchicine be tapered and withdrawn within 15 days after entry into the EP. It is encouraged that corticosteroids be progressively tapered (e.g., by 5 mg prednisone or equivalent every week in adults or 0.2mg/kg every week in subjects <18yo) and discontinued within 6 weeks after entering to EP (i.e., by Study Week 12) unless in the opinion of Investigator, a different corticosteroid weaning schedule is required based on subject’s clinical status. Other pericarditis medications may also be initiated at the discretion of the Investigator. All changes to pericarditis-related medications should be captured in the source records and eCRF

Unscheduled clinic visits can be scheduled any time as determined by the Investigator/upon subject request. In addition, Investigators are encouraged to schedule subjects at the Study Site/Clinic for an in-person Interval Evaluation Visit between Weeks 15 to 20 (8 to 13 weeks after Visit 7) to assist the Investigator in the clinical management of the subject. During this visit a physical examination, vital signs, ECG, echocardiogram, and laboratory testing can be performed. However, this visit is not mandatory, and therefore not all subjects will have it.

Subject-reported pericardial pain evaluations using a validated 11-point NRS instrument as well as AE monitoring will be performed during the EP at on-site clinic visits and/or during monthly Investigator (or designee) phone calls/virtual visits. A subject-reported QoL questionnaire will be administered at the Interval Evaluation Visit and the Final Visit of the EP. At the end of the EP, subjects will complete the Week 25/Final Visit.

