- c. Weekly intervals refer to  $7 \pm 1$  days. The interval between Study Drug administrations must be at least 5 days.
- d. Subjects should return for an optional Interval Evaluation Visit at the clinic between approximately Week 3 and 4, as determined by the Investigator.
- e. Including age at first attack, number of previous attacks, and duration of attacks.
- f. Drug administration training of subjects is performed at Visit 1. Study Drug will be administered in the Study Site/Clinic at Visit 1. Study Drug administrations are performed by the subjects (self-administration) on Visits (Outpatient) 2, 3, 4, 5, and 6. Participation in the Extension Phase (optional) is determined at the Week 6/EoT Visit 7 by the Investigator. Subjects who are eligible and who are willing to participate will be consented during EoT Visit 7 at the Study Site/Clinic. Only subjects continuing treatment into the Extension Phase will receive Study Drug at Visit 7; Study Drug can be self-administered either as an outpatient or at the Study Site/Clinic (Site to provide Study Drug) depending on the logistics/timing of the EoT Visit 7 relative to the timing of weekly dosing. Timing for dose administration is per direction of the Investigator based upon the prescribing information and study-specified dosing intervals. Continued weekly Study Drug treatment during the EP will be outpatient administration.
- g. Full physical examination including assessment of pericardial rub.
- h. Vital signs must be obtained in the seated position and include oral temperature, respiratory rate, blood pressure, and pulse.
- i. Central 12-lead ECG and echocardiogram reading (including assessment of pericardial effusion). At SCV2 only the ECG will be obtained. The Study Site/Clinic reading of the ECG and the ECHO at the time of the examination will be used by the Investigator for clinical decision-making. In addition, both the ECG and ECHO will be sent to a core laboratory for additional analysis.
- j. Optional in Group 1 and 3. Required for Group 2.
- k. At the SCV1, information related to concomitant medicine that subjects were taking during at least the 2 weeks prior to the visit will be captured. During the Treatment Period, changes in concomitant medication since the last Study Site/Clinic visit will be documented. During the EP, changes in pericarditis/concomitant medication will be assessed at Study Site/Clinic Visits and in monthly outpatient phone calls/virtual visits.

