- l. Biomarker, pharmacokinetics (PK) and anti-rilonacept antibody analysis samples will be drawn in all subjects and archived for future testing. During each Visit at the Study Site/Clinic a sample for CRP will be obtained and sent to the central laboratory (or designated qualified laboratory) for analysis; at each Outpatient Visit; blood for central laboratory measurement of CRP will be obtained as described in the Laboratory Manual.
- m. Hematology, chemistry, and urinalysis will be performed at the Study Site/Clinic laboratories, and results when available will be entered into the eCRF with appropriate reference values. Serology (HCVAb, HBsAg, HBcAb, HBsAb and HIV) and urine drug screen will be performed at SCV1 only.
- n. To be eligible to continue in the trial, a negative urine pregnancy test must be documented at the SCV1. If the urine test is positive, additional Study Site/Clinic and/or central serum tests may be performed.
- o. All AEs occurring after the subject receives the first dose of Study Drug will be captured in source records and eCRF.
- p. At the SCV1, the Investigator or designee will instruct the subject about the use of the medication diary. The subject will be asked to complete entries into the medication diary during the Screening Period and Treatment Period. Only information on pain/rescue medication will be collected. Other concomitant treatments/medications are not required to be captured.

- q. At the SCV2 and all subsequent visits at the Study Center, the Investigator or designee will review the Diary entry information to verify subject compliance. If the last screening visit occurs at a different day than Visit 1, the review will also be performed at Visit 1. Diary documentation will end at the End-of-Trial visit (Visit 7).
- r. Subject assessment of pericardial pain using a validated 11-point Numerical Rating Scale. The assessment will be performed on-site during clinic visits and as part of a telephone call/virtual visit during outpatient treatment weeks. If the last screening visit occurs at a different day than Visit 1, the assessment will also be performed at Visit 1, prior to Study Drug treatment.

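### Time to first pain/rescue medication runs to study end, although the rescue diary stops at Visit 7 and later use is less intensively ascertained

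*SAP*

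**What the plan says.** SAP Section 5.4.10.7 defines time to first pain/rescue medication as the earliest post-baseline study day of use. For subjects without any use, "it will be censored at the study day of study completion/discontinuation". It plans one Kaplan-Meier analysis over the whole study, giving the median and the 25% and 75% percentiles with 95% confidence intervals. It also gives the percentage of subjects with any use in the Treatment Period, the Extension Period and the entire study, by medication type as recorded on the eCRF. As-needed use counts.

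The data sources are in the footnotes to the Schedule of Evaluations (Section 8.1):

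- Footnote p, on when the diary is kept: "The subject will be asked to complete entries into the medication diary during the Screening Period and Treatment Period". On its content: "Only information on pain/rescue medication will be collected".
- Footnote q, on when it stops: "Diary documentation will end at the End-of-Trial visit (Visit 7").
- Footnote k, on what follows: "During the EP, changes in pericarditis/concomitant medication will be assessed at Study Site/Clinic Visits and in monthly outpatient phone calls/virtual visits".
- Footnote v: contacts are weekly in the Treatment Period, with a check on diary compliance, and monthly in the Extension Period, with a review of medications.

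Section 2.2 gives the duration: "The EP is defined as the 18 weeks following the Treatment Period". It also asks that changes to pericarditis-related medication be entered in the source records and eCRF during that period. Section 5.4.10.7 does not mention the change of method at Visit 7 and gives no rule for dating as-needed use afterwards.

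**The concern.** Kaplan-Meier estimation treats every day before censoring as a day on which an event would have been seen. Here the dedicated instrument stops and the contact interval lengthens at the same visit, while the risk set carries on unchanged. The event is also easy to miss: one as-needed dose is enough, and a single dose taken between monthly calls may be forgotten or misdated. The Extension Period review is worded around changes in medication, which does not clearly cover an isolated analgesic dose.

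A missed dose turns an event into a later event or a censored time, so missed doses can only push the estimated times later. The same loss lowers the Extension Period percentage. A reader who sees that percentage beside the Treatment Period figure could take a drop at Visit 7 for a clinical change when part of it is a change in recording.

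**Working it through.** The SAP states no event rate or expected quantile for this endpoint, so there is no planned figure to reproduce. The check has two parts.

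**Share of follow-up after the diary ends.** Section 2.2 gives 18 weeks of Extension Period within a total of 24 weeks: 18/24 = 75%. By the visit labels in Section 8.1 (final visit at Week 25, end of the Treatment Period at Week 6 or 7), it is (25 − 6)/25 = 76% or (25 − 7)/25 = 72%. These shares apply only to subjects who complete the Extension Period.

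**Effect on the curve.** Two inputs are assumed, because the SAP gives neither: a constant weekly probability of use *h*, and a proportion *s* of Extension Period use that is captured. Diary capture is taken as complete.

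- True 24-week cumulative use: 1 − (1 − h)^24
- Use shown by the planned curve: 1 − (1 − h)^6 × (1 − h·s)^18

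For h = 0.03:

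- True: 1 − 0.97^24 = 1 − 0.481 = 52%
- s = 0: 1 − 0.97^6 = 1 − 0.833 = 17%
- s = 0.5: 1 − 0.833 × 0.985^18 = 1 − 0.833 × 0.762 = 37% (0.365 before rounding)
- s = 0.75: 1 − 0.833 × 0.9775^18 = 1 − 0.833 × 0.664 = 45%
- s = 1: 52%, no bias

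For h = 0.01, true use is 1 − 0.99^24 = 21%. The curve shows 1 − 0.99^6 = 6% at s = 0, 1 − 0.941 × 0.995^18 = 1 − 0.941 × 0.914 = 14% at s = 0.5, and 21% at s = 1.

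**Effect on the planned quantiles.** At h = 0.03:

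- The true 25% percentile is ln(0.75)/ln(0.97) = 9.4 weeks. At half capture it becomes 6 + ln(0.75/0.833)/ln(0.985) = 12.9 weeks. At zero capture it is not reached.
- The true median is ln(0.5)/ln(0.97) = 22.8 weeks. At three-quarters capture or less it is not reached, since the curve stops at 45% or below.

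At h = 0.01 no planned quantile is reached even with full capture, so the bias would not show in the reported quantiles.

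**Cross-check with a continuous constant hazard**, set by the true 24-week use:

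| True 24-week use | By Week 6 (also shown at Week 24 if s = 0) | Shown, s = 0.5 | Shown, s = 0.75 | Shown, s = 1 |
|---|---|---|---|---|
| 50% | 15.9% | 35.2% | 43.1% | 50% |
| 70% | 26.0% | 52.9% | 62.4% | 70% |

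In the 70% case the median is not reached at s = 0, and is 21.6, 16.4 and 13.8 weeks at s = 0.5, 0.75 and 1. Direction and size agree with the weekly calculation.

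**Extension Period percentage.** With h = 0.03, true use over the 18 weeks is 1 − 0.97^18 = 42%. At half capture the table would show 1 − 0.985^18 = 24%.

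**The case against.** The strongest reply is that the diary is not the only source. Medication is reviewed at monthly calls and clinic visits, changes to pericarditis-related medication go into the eCRF, and Section 5.4.10.7 ties its medication types to the eCRF rather than to the diary. Subjects in the Extension Period are still under observation, so censoring at study end is a defensible rule. This stands. A reader might infer from the end of the diary that Extension Period rescue use goes unrecorded. The documents do not support that: the time is observed less closely, but it is observed. Zero capture is therefore a bounding case and not an expectation.

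Second, the constant rate is only an assumption. Parts 1, 2 and 4 enrol symptomatic subjects, and the extension is optional and restricted: "Subjects who are considered to be “Treatment Responders” will be, at the discretion of the Investigator, offered participation in an optional 18-week EP". First use may cluster in the weeks that the diary covers, which would shrink the effect. This also stands. In the other direction, Section 2.2 encourages tapering of background medication in the Extension Period, just when capture is weaker.

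Third, a reader might conclude that the whole-study curve should be replaced by one ending at Visit 7. That would discard collected events and leave little to report. At 3% and 1% per week, only 17% and 6% have an event by Week 6, so none of the three planned quantiles would be reached. Replacement is not warranted.

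Fourth, Extension Period use is already tabulated separately, and Section 5.1 makes the analyses descriptive. No formal comparison of the two periods is planned, and such a comparison would be unsafe anyway because the extension holds selected responders. What remains is that the tables and the curve carry no sign that the method of ascertainment changed.

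**Conclusion.** The point holds in a limited form. The planned curve gives diary-covered time and monthly-review time the same weight, and about three quarters of an Extension Period completer's follow-up is of the second kind. Times to first use are likely biased long and Extension Period percentages likely low.

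The size cannot be fixed from the SAP. Under the assumed 3% per week and complete diary capture, 24-week use of 52% would show as anything from 17% to 52% as Extension capture goes from none to full; under 1% per week, 21% would show as 6% to 21%. Missed doses bias in one direction only, but misdating a recalled dose could go either way.

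It would be too strong to say that the quantiles are certainly wrong. With full capture there is no bias from this source, and at a low rate of use no quantile is reached at all. The summary is descriptive and sits outside the primary endpoints of an open-label pilot, so no error rate, sample size or primary conclusion depends on it. It is worth correcting because the correction is cheap and needs no new data.

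**What to change.** In Section 5.4.10.7:

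1. Add a diary-based Kaplan-Meier analysis of time to first pain/rescue medication, censored at the earlier of Visit 7 and discontinuation. Report the cumulative estimate at Week 6 with its 95% confidence interval, because the quantiles may not be reached.
2. Keep the whole-study curve as supportive. Label it as combining diary ascertainment up to Visit 7 with medication review at monthly calls and clinic visits afterwards.
3. Footnote the Treatment Period and Extension Period percentages in the same way.

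The cost is a few sentences of SAP text and one extra descriptive analysis. It will be imprecise: if all of the approximately 40 planned subjects contributed, the assumed rates would give about 40 × 0.167 = 7 or 40 × 0.059 = 2 events by Week 6, and fewer in any single Part.
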